**Data Analysis:**

We consulted with [name] through the Harvard Catalyst statistical consultation service for assistance with study design and sample size calculations. A project statistician will assist with statistical analyses.

**Delayed Gastric Emptying Substudy**

Preliminary data from our main study includes 41 individuals randomized to exenatide and 9 randomized to placebo. There is no difference in resting energy expenditure between exenatide and placebo-treated subjects. However, there are significant differences in TEF at 1 hour ( $p < 0.009$ ), 2 hours ( $p < 0.03$ ) and 4 hours ( $p < 0.04$ ) postprandially. According to these data, we expect to observe a detectable difference in total TEF of about 674 kcal (SD 570 kcal) before and after treatment with morphine. A sample size of 12 individuals will have 80% power to detect this difference at a significance level of 5%. Student's t-test will be used to determine if morphine significantly suppresses TEF compared to baseline and compared to exenatide treatment.

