### **Delayed Gastric Emptying Substudy**

Delayed gastric emptying is a known effect of exenatide treatment. Delayed gastric emptying can cause early and prolonged satiety, both of which may contribute to exenatide-induced weight loss. There is no literature on the effect of delayed gastric emptying on energy expenditure, in particular the thermic effect of food. Preliminary data from this study indicate that exenatide treatment is associated with a blunting of the thermic effect of food. This blunting is seen among exenatide responders (> 5% weight loss after 3 months of treatment) and among nonresponders (< 5% weight loss at 3 months). In contrast, individuals assigned to the placebo group maintain a 100-300 calorie increase in resting energy expenditure (the thermic effect of food, TEF) even in the setting of weight loss comparable to exenatide responders.

These intriguing data are the rationale behind a substudy that will further examine the effect of delayed gastric emptying on TEF. This substudy will specifically examine the effect of low-dose morphine, an agent that also delays gastric emptying, on TEF. By studying another agent known to delay gastric emptying through a different pharmacologic mechanism, we can determine whether the blunted TEF that we see with exenatide is due to delayed gastric emptying or another mechanism of action of exenatide. For the substudy, we will recruit women who have completed treatment in the main study, either at 3 months (nonresponders) or at 12 months (responders). As mentioned, we have observed a blunting in TEF among both responders and nonresponders to exenatide, indicating that this effect is due to exenatide and independent of weight loss. Our current study population excludes women with diabetes or gastroparesis, both of which we also want to exclude in this substudy.

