  - 24-hr food recall
  - Assessment of symptoms, adverse events, and diet/medication compliance
  - Resting energy expenditure
  - Physical activity monitoring if device is available
- **10% Weight Loss Procedures**
  - Fasting lipid panel
  - Fasting leptin, soluble leptin receptor, insulin, cortisol, adiponectin, CRP, FGF21 levels
  - Standard measurements
  - VAS for nausea, satiety, hunger
  - 24-hr food recall
  - Assessment of symptoms, adverse events, and diet/medication compliance
  - Resting energy expenditure
  - Physical activity monitoring if device is available
- **15% Weight Loss Procedures**
  - Fasting lipid panel
  - Fasting leptin, soluble leptin receptor, insulin, cortisol, adiponectin, CRP, FGF21 levels
  - Standard measurements
  - VAS for nausea, satiety, hunger
  - 24-hr food recall
  - Assessment of symptoms, adverse events, and diet/medication compliance
  - Resting energy expenditure
  - Physical activity monitoring if device is available
- **15% % Weight Loss Procedures (20%, 25%, 30% etc)**
  - Fasting lipid panel
  - Fasting leptin, soluble leptin receptor, insulin, cortisol, adiponectin, CRP, FGF21 levels
  - Standard measurements
  - VAS for nausea, satiety, hunger
  - 24-hr food recall
  - Assessment of symptoms, adverse events, and diet/medication compliance
  - Resting energy expenditure
  - Physical activity monitoring if device is available
- **Substudy Procedures**
  - Overnight fast
  - Urine pregnancy test if applicable
  - Standard measurements
  - Measurement of baseline resting energy expenditure
  - Administration of a single dose of morphine, 0.05mg/kg
  - Oral ingestion of Boost (mixed meal)
  - Measurement of TEF hourly for 4 hours with indirect calorimetry
  - Vital signs every 30 minutes following administration of morphine and prior to discharge from CRC

The 5%, 10%, 15%, and > 15% weight loss procedures will not occur within 2 weeks of starting the treatment, as acute weight loss within this time frame is likely due to fluid shifts rather than fat loss.

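### The morphine substudy's only criterion is t-test significance in 12 women, which cannot show that morphine reproduces exenatide's effect on the thermic effect of food or settle the mechanism

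*Combined protocol and SAP*

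**What the plan says.** In section B1, Delayed Gastric Emptying Substudy, the rationale is that morphine delays emptying by a different pharmacological route, so that "we can determine whether the blunted TEF that we see with exenatide is due to delayed gastric emptying or another mechanism of action of exenatide".

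Section B3.B, under the same heading, gives the statistics. The planning effect is "a detectable difference in total TEF of about 674 kcal (SD 570 kcal) before and after treatment with morphine", and 12 individuals "will have 80% power to detect this difference" at the 5% level. The effect is derived from exenatide and placebo data, not morphine data: "Preliminary data from our main study includes 41 individuals randomized to exenatide and 9 randomized to placebo". The analysis is one sentence: "Student's t-test will be used to determine if morphine significantly suppresses TEF compared to baseline and compared to exenatide treatment".

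The procedures are in section B3.A (Gastric Emptying Substudy, and Substudy Procedures under Study Visits). They list resting energy expenditure, "Administration of a single dose of morphine, 0.05mg/kg", the mixed meal, TEF by indirect calorimetry, and vital signs. Gastric emptying is not on either list.

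The plan does not state:
- whether the tests are paired;
- whether 570 is a between-woman SD or an SD of within-woman differences;
- any sizing or SD for the contrast with exenatide;
- a similarity margin or an interval rule;
- how a non-significant result will be interpreted.

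**The concern.** The mechanistic question has two natural answers. The first, that delayed emptying accounts for the blunting, needs morphine to do about what exenatide does, which is a similarity claim. The second, that another mechanism is at work, needs morphine to do little or nothing, which is an absence claim. A t-test for a difference controls the error rate of neither. Significance against baseline shows some suppression, not that it matches exenatide's. Non-significance against exenatide may only mean that the comparison is imprecise.

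Separately, without an emptying measurement, a null result cannot distinguish a dose that failed to delay emptying from delayed emptying that does not affect TEF. A positive result cannot show that emptying was the route by which morphine acted. Choosing between mechanisms is the substudy's stated purpose, so its main conclusion is at stake. The main-trial weight analyses are not affected.

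**Working it through.** **Inputs** (B3.B, Delayed Gastric Emptying Substudy): difference 674 kcal, SD 570 kcal, 12 women, 80% power, 5% level, 41 exenatide women in the preliminary data. Assumptions: two-sided tests; 570 also applies to morphine versus exenatide; where women are paired and 570 is a between-woman SD, a within-woman correlation of 0 to 0.5.

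**The plan's own figure.** For two independent groups, n per group = 2 × (1.960 + 0.842)² × (570/674)² = 2 × 7.85 × 0.715 = 11.2, rounded up to 12. Noncentral-t power at 12 per group is 0.79. So 12 with 80% power reproduces, but as 12 per group unpaired. A paired test with an SD of differences of 570 would need 8 women (power 0.82) and would have power 0.96 with 12. Twelve in total, as 6 versus 6, would have power 0.46.

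**Morphine versus exenatide.** The 95% half-width is t(0.975, df) × SE. The miss rate is 1 minus noncentral-t power for a true shortfall of 337 kcal (674/2).

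| Layout | SE | t | Half-width | Share of 674 | Miss rate |
|---|---|---|---|---|---|
| Paired, SD of differences 570 | 570/√12 = 164.5 | 2.201 | 362 | 54% | 54% |
| 12 v 41 | 570 × √(1/12 + 1/41) = 187.1 | 2.008 | 376 | 56% | 58% |
| 12 v 12 | 570 × √(2/12) = 232.7 | 2.074 | 483 | 72% | 72% |
| Paired, correlation 0 (SD of differences 570√2 = 806) | 806/√12 = 232.7 | 2.201 | 512 | 76% | 74% |

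The first row also corresponds to a between-woman SD of 570 with correlation 0.5, because 570 × √(2 × 0.5) = 570.

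**Could the design show similarity?** The table gives simulated power of two one-sided 5% tests when morphine and exenatide are truly equal. The margins are illustrative, since the plan names none.

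| Margin | Paired, 570 | 12 v 41 | 12 v 12 | Paired, 806 |
|---|---|---|---|---|
| 25% (168.5 kcal) | about 0 | about 0 | about 0 | about 0 |
| 50% (337 kcal) | 25% | 12% | 2% | 3% |
| 75% (505.5 kcal) | 78% | 69% | 36% | 33% |

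Requiring a 95% interval inside the margin is stricter than these tests, so its chances are lower still. For 80% power at the 50% margin, about 26 women paired (SD 570) or 50 per group would be needed.

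**Morphine versus baseline.**

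| True suppression | Paired, 570 | Paired, 806 | 12 v 12 |
|---|---|---|---|
| 674 (full) | 96% | 75% | 79% |
| 337 (half) | 46% | 26% | 28% |
| 168.5 (quarter) | 15% | 10% | 11% |

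All the half-widths are below 674, so an estimate near zero would exclude full suppression. It would leave suppression of about half or more open.

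**Which layout is possible?** The substudy session has one meal, given after morphine, so the comparison TEF must come from main-study records. TEF is measured only in a subset there (B1, Outcome measurements). B1 recruits women who completed main-study treatment without expressly requiring the exenatide arm. A woman's own on-exenatide TEF may therefore not exist.

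**The case against.** Much of the opposing case is sound.

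- A reader might infer that the protocol commits itself to treating a null result as proof. It does not. B1 offers a rationale and B3.B names a test; neither says how non-significance will be read. The defect is that nothing is specified.
- A reader might also infer that 12 women can say nothing about absence of suppression. That is too strong: power for the full 674 kcal against baseline is 75% to 96%, so full suppression can be excluded.
- The plan attaches 570 kcal to the before-and-after morphine difference and gives no SD for morphine versus exenatide. Using 570 there is borrowed, and the half-size shortfall is an illustrative scenario. The results are ranges under assumptions. At 12 v 41, which uses the exenatide women already reported, the miss rate is 58%, towards the lower end.
- B1 relies on morphine as an agent already known to delay emptying, and the reference list includes a low-dose morphine gastric-emptying study in healthy volunteers. Whether that study is enough cannot be judged from these documents. Even if it is, it would not show that emptying was delayed in these women at this session.
- Expressing morphine's suppression as a fraction of exenatide's in the same women, against a fixed 50% threshold, is not a ready solution. The fraction may not exist for every woman. If morphine truly reproduced the whole effect, the lower 95% limit would exceed 50% only 39% to 58% of the time (both suppressions with SD 570, correlation 0 to 0.5). The threshold itself is debatable.
- This is a small add-on that leaves the main analyses untouched.

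These points narrow the concern. None supplies the missing rule for the exenatide contrast.

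**Conclusion.** The concern holds in this limited form. The plan says the substudy can determine the mechanism, but its only criterion is significance of a difference. For morphine versus exenatide there is no margin, interval rule or sizing. If the SD of 570 kcal carries over, the 95% interval spans 54% to 76% of the full effect on each side, and a half-size shortfall is missed 54% to 74% of the time. For morphine versus baseline, full suppression can be excluded but partial suppression cannot (26% to 46% power for half). Because emptying is not measured, neither a null nor a positive result establishes the mechanism by itself, whatever the sample size.

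The documents do not support saying that the sample size is arithmetically wrong. Twelve reproduces as a per-group number, and the gap is that pairing and the type of SD are unstated.

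The ratio-based figures do not depend on the unit. However, the 674 kcal is not reconciled with the 100 to 300 calories that B1 gives for TEF in placebo women. If true suppression were 100 to 300 kcal with an SD of differences of 570 to 806, power against baseline would be only 7% to 38%. This should be corrected, but it bears on the substudy's conclusion only.

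**What to change.** In B3.B, Delayed Gastric Emptying Substudy:

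1. Base conclusions on the estimated difference and 95% interval for morphine versus baseline and for morphine versus exenatide, not on significance.
2. Make the exenatide contrast paired only in women with their own on-exenatide TEF record. Otherwise make it unpaired against the main-study exenatide TEF data. State the pairing of the baseline contrast and what kind of SD 570 is.
3. Claim similarity only if the interval versus exenatide lies within a margin that the sponsor prespecifies and justifies. Claim absence of full suppression only if the interval versus baseline excludes it. Otherwise report the result as inconclusive.
4. Reconcile the TEF window, since total TEF depends on it: section B3.A allows up to six hours in the substudy description and four in the procedures list. Explain how 674 kcal relates to the 100 to 300 calories in B1.

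In B1, reword the aim as testing whether morphine reproduces the TEF blunting. Add that a null result does not show another mechanism, and that a positive one is only consistent with delayed emptying.

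The cost is wording and two intervals, with no added women or procedures. The drawback is that with 12 women an inconclusive result is likely, and the plan should say so.

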#### *Outcome measurements:*

*Weight:* We will compare the duration and magnitude of weight loss among exenatide responders with the

duration and magnitude of weight loss among subjects assigned to placebo with a calorie-restricted diet over 52 weeks. We will also compare changes in weight at 3 and 6 months after the cessation of exenatide treatment or diet. Weight loss will be correlated to baseline BMI.

**Body composition:** Baseline body composition may predict response to exenatide treatment, and weight loss with exenatide may be associated with decreased fat versus lean body mass compared to diet-induced weight loss. We will compare the effect of exenatide treatment versus caloric reduction on body composition over 52 weeks using bioelectrical impedance analysis (BIA) and by measuring waist circumference.

**Resting energy expenditure (REE):** Our initial data suggest that exenatide may blunt the decrease in resting energy expenditure that is typically associated with diet-induced weight loss. We will measure resting energy expenditure (REE) via indirect calorimetry at baseline, at weeks 12, 24, and 52, and after 5%, 10%, 15% weight loss is achieved, and at additional 5% weight loss timepoints, as applicable (i.e., 20%, 25%, etc).

**Mixed meal test:** Exenatide may improve beta cell function and lower postprandial triglycerides in nondiabetic individuals. Measurement of fasting insulin and triglyceride levels does not capture these effects. We will administer a mixed liquid meal (Boost) and measure serial postprandial insulin, , and triglyceride levels. Subjects will have a mixed meal test at baseline, and at weeks 12, 24, and 52.

**Thermic effect of food:** Exenatide treatment may result in an increase in the thermic effect of food, which could explain, at least in part, why we did not see a significant reduction in energy expenditure among exenatide high responders in our initial study. We will measure the thermic effect of food using indirect calorimetry following the mixed meal challenge. Energy expenditure will be measured for 15-20 minutes every hour for four hours after the mixed meal challenge. The thermic effect of food will be measured in a subset of subjects at baseline, and at weeks 12, 24, and 52.

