**Gastric Emptying Substudy**

Subjects, all of whom met eligibility criteria for and participated in the main study, will report to the CRC after an overnight fast. Women of childbearing potential (menstrual period within the past 2 years) will have a urine

pregnancy test. After vital signs are obtained, including weight, blood pressure, heart rate, and oxygen saturation, we will place an IV and subjects will rest for 15-20 minutes. After this rest period we will measure baseline resting energy expenditure using indirect calorimetry. Subjects will then receive a single bolus dose of IV morphine, 0.05mg/kg, followed by a mixed meal challenge (single serving of Boost). We will measure the thermic effect of food using indirect calorimetry for 15-20 minutes every hour for up to six hours after the mixed meal challenge, as is done in the main study. Subjects will have vital signs monitored every 30 minutes following administration of morphine and immediately prior to discharge from the CRC. Subjects will not be permitted to drive home after discharge, they will either have a ride or will be provided with compensation for transportation.

All adverse events reported spontaneously by the subject, as well as those noted by the investigator or study site staff, will be recorded. In order to avoid vague, ambiguous, or colloquial expressions, the adverse event term will be recorded using standard medical terminology rather than the subject's own words. Every attempt will be made to describe the adverse event in terms of a diagnosis. Whenever the investigator is confident in making a unifying diagnosis, all related signs, symptoms and abnormal test results should be grouped together and recorded as a single adverse event.

All subjects who have adverse events, whether or not the adverse events are considered associated with the use of the study medication, will be monitored until the adverse event resolves, stabilizes, or becomes chronic. The clinical course of the adverse event will be followed according to accepted standards of medical practice, even after the end of the observation period, until a satisfactory explanation for the adverse event is found or the investigator considers it medically justifiable to terminate follow-up. All adverse events will be evaluated for intensity and causal relationship with use of the study medication.

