*Visual Analog Scales:* Visual analogue scales are used to measure subjective satiety and hunger (Cornier et al., 1994). Satiety will be defined as the sensation of fullness after eating so that a person does not feel the need to eat for some time afterward. Hunger will be defined as the subjective driving force for the search for, choice of, and ingestion of food. Subjects will be instructed to make a single vertical mark on a horizontal 10-cm bar to indicate their current feelings, ranging between "not hungry at all" and "really hungry", between "empty" and "full" and between "not at all nauseated" and "extremely nauseated." Subjects will complete the VAS the day prior to the study visit, once in the morning in the fasted state and a second time 2 hours after eating their evening meal. The visual analog packet will also include questions about eating habits, including overeating and binge eating. The entire packet will take less than 5 minutes to complete.

*Resting energy expenditure:* Indirect calorimetry calculates heat production by measuring gas exchange. During resting conditions, food sources are broken down to produce energy (heat or KCALS). The oxygen consumed and the carbon dioxide produced are measured to provide an indirect assessment of caloric expenditure. Resting energy expenditure (REE) provides the total energy expenditure in 24 hours and is calculated from the gas exchange data (VO2, VCO2) collected by the Vmax. When obtaining a subject's REE, the subject reaches a steady state condition, which is defined as five consecutive minutes in which the VO2 and VE are within 10% and the RQ (respiratory quotient) is within 5%. Subjects in the fasted state will lay face up on an examination bed for approximately 20-30 minutes with a mask over the nose and mouth while measurements of gas exchange are taken. The use of indirect calorimetry to measure REE has been used as a measure of energy expenditure in clinical studies with obese subjects (Perseghin, 2001; Smith et al., 2005).

*Mixed meal test:* After an overnight fast, subjects will consume a standardized liquid test meal containing 35% of their calculated 24-hour energy requirements distributed as 40% of total calories from fat, 40% from carbohydrate, and 20% from protein. After the meal, serum insulin and triglyceride levels will be measured.

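### The morphine substudy can compare TEF only with main-study meal tests, but the protocol gives conflicting test meals and measurement windows and does not require recruits to have a comparator

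*Combined protocol and SAP*

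**What the plan says.** All references are to the combined protocol and SAP.

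- **Session.** In B3.A, Gastric Emptying Substudy, the only energy measurement before morphine is fasting: "After this rest period we will measure baseline resting energy expenditure using indirect calorimetry". Morphine is then given, "followed by a mixed meal challenge (single serving of Boost"). The Substudy Procedures list under Study Visits has the same order.
- **Contrasts.** B3.B, Delayed Gastric Emptying Substudy, says that Student's t-test "will be used to determine if morphine significantly suppresses TEF compared to baseline and compared to exenatide treatment".
- **Meal.** The substudy uses one serving of Boost. For the main study, B3.A, Explanations of measurements and assessments, describes a "standardized liquid test meal containing 35% of their calculated 24-hour energy requirements", with fixed shares of fat, carbohydrate and protein. B1, Outcome measurements, says "We will administer a mixed liquid meal (Boost") and gives no amount.
- **Window.** The substudy text measures TEF "every hour for up to six hours after the mixed meal challenge, as is done in the main study". B1, Outcome measurements, the Substudy Procedures list and the TEF paragraph of the Explanations all give four hours.
- **Availability.** B1 and the Explanations restrict main-study TEF to a subset of subjects. The visits are baseline and weeks 12, 24 and 52.
- **Sample size.** B3.B states: "we expect to observe a detectable difference in total TEF of about 674 kcal (SD 570 kcal) before and after treatment with morphine". It continues: "A sample size of 12 individuals will have 80% power to detect this difference at a significance level of 5" per cent.

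**The concern.** The substudy is meant to show whether the blunted TEF seen on exenatide comes from delayed gastric emptying or from some other action of the drug. Its single session contains no control meal, so the answer depends on how closely that session matches the main-study sessions used as comparators.

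TEF is a response to a meal. If the morphine session uses a fixed serving and the comparator sessions used a meal scaled to the woman, the contrast mixes morphine with meal energy. A smaller substudy meal would look like suppression and appear to support the gastric-emptying explanation. A larger one would hide a true effect. No analysis of these sessions could separate the two.

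A total over six hours set against a total over four would distort the contrast in a similar way. A recruit from outside the TEF subset would have no comparator of her own.

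**Working it through.** **1. Where the comparators come from.** Fasting REE is not TEF, and the substudy schedules no meal without morphine and none on exenatide. The only TEF values available for either contrast are those from main-study meal tests at weeks 0, 12, 24 and 52. This is an inference from the procedure lists, but no other source is scheduled.

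**2. Meal.** One serving is a fixed amount. A meal of 35% of the daily requirement varies between women. The two can coincide only by chance. The B1 text names Boost without an amount and is compatible with either, so the conflict is between two passages. The energy of a serving is not given, so neither the direction nor the size of any bias can be calculated.

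**3. Window.** One passage gives up to six hours and attributes this to the main study. Three places give four hours. Hours 0-4 are common to all of them, so this conflict can be resolved from the hourly readings if the hours to be totalled are fixed beforehand.

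**4. Who has a comparator.** B1, Delayed Gastric Emptying Substudy, recruits women finishing main-study treatment at 3 months (nonresponders) or 12 months (responders). It does not require membership of the TEF subset. Its context is exenatide, but B3.A, Overview, applies the responder labels to placebo as well, so the arm should be stated. Exenatide nonresponders leave at week 12 (B3.A, Study duration), so that is their only on-exenatide TEF visit. Responders may also have weeks 24 and 52.

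**5. The stated sample size.** Inputs from B3.B: difference 674 kcal, SD 570 kcal, 12 individuals, 80% power, 5% level. Two-sided testing is assumed. Standardised difference: 674/570 = 1.18.

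- *Two independent groups, normal approximation:* n per group = 2 × (1.960 + 0.842)² × (570/674)² = 11.2, rounded up to 12. With the noncentral t, 12 per group gives power 0.79. This reproduces the plan's figure.
- *12 pairs, 570 as SD of the change:* noncentrality 674/(570/√12) = 4.10 on 11 df; power 0.96. Eight pairs would suffice for 80%.
- *12 pairs, 570 as single-session SD:* SD of the change = 570 × √(2(1 − ρ)). At ρ = 0 this is 806 kcal and power is 0.75. At ρ = 0.115 power is 0.80. At ρ = 0.5 the SD of the change is 570 kcal and power is 0.96. The correlations are assumptions.

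The stated 12 therefore matches a calculation with 12 per group, whereas the text describes one cohort before and after morphine. The preliminary data quoted there compare 41 exenatide with 9 placebo subjects, which does not settle what 570 measures.

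**The case against.** The strongest reply is that much of this is clear in context. Baseline TEF most naturally means week 0. The wording about 12 individuals before and after morphine points to one cohort and a within-woman comparison. B1 already describes TEF as an increase over resting expenditure. The statement that the main study does the same may refer to the hourly 15-20 minute method and not to six hours, and up to six hours includes four. This is also a small mechanistic substudy outside the main analyses.

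Most of that stands. What remains open is the on-exenatide visit, how the hourly readings form a total, what 570 measures, and the meal. The meal conflict is not removed by any reading of context.

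Stronger readings are tempting but not supported:

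- **That the substudy is underpowered.** Power for 12 pairs runs from 0.75 to 0.96 over the readings shown, and the low end needs a correlation of zero. The basis is unstated; a shortfall is not shown.
- **That the result will be biased.** If the main study used the same single serving, the meal bias is absent. The documents do not say which meal was given in practice.
- **That a false-positive rate can be attached to the mismatch.** This would need the energy of a serving, which is not given.
- **That week 12 is the only proper exenatide comparator.** All recruits share it, but for responders it is about nine months old when they enter. Each woman's last on-exenatide TEF is also a single rule and is closer in time.

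**Conclusion.** The point holds for the meal, the window and the availability of comparators. Both contrasts rest on main-study sessions. Following the two meal descriptions as written would confound meal energy with morphine, by an amount and in a direction that the documents do not allow one to calculate. The window conflict is real but recoverable. Nothing ensures that recruits have a TEF value at the comparator visits.

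The missing statements on pairing and on the SD are gaps in specification. They make the stated power uncheckable for the design described, but they do not show that 12 women are too few. The conclusion assumes that no unlisted control meal is given in the substudy; the power figures assume two-sided testing.

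**What to change.** - **Meal.** Reconcile B1, Outcome measurements, with the B3.A substudy text, Substudy Procedures list and Explanations, so that each woman's substudy session uses the same test meal, in the same amount, as her comparator sessions. The protocol does not say whether the 35% is recalculated after weight loss. If her main-study meals differed between visits, state which one is matched and report the difference.
- **Endpoint.** Define total TEF over hours 0-4 as the increment over that session's fasting REE, and state how the hourly readings are combined. Treat later hours as exploratory.
- **Recruits.** In B1, limit recruitment to exenatide-arm women with main-study TEF at the comparator visits.
- **Test.** In B3.B, specify a paired t-test for each contrast, with week 0 as baseline. Fix one on-exenatide rule before the data are seen: week 12 for all, or each woman's last on-exenatide TEF, with the other as a sensitivity analysis.
- **Power.** Restate it for 12 complete pairs and say what SD 570 kcal is.

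No visit is added. Caloric requirements are already calculated at enrollment (B3.A, Dietary counseling), so either meal definition can be repeated. If the main study used the scaled meal, however, matching changes the substudy procedure as well as the wording. The other costs are a narrower recruitment pool and the loss of hours five and six from the main endpoint. The comparators also remain historical: in responders the week 0 session is about a year earlier and at a higher weight, and matching the meal does not remove that.
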